7.1.4. Characteristics of exposure

Women can be intentionally or unintentionally exposed to vaccines during pregnancy. In general, the women are closely monitored throughout the remainder of the pregnancy.

Refer to Section 9.2.1.2 for potential annual exposure in pregnant women.

7.1.5. Potential benefits of product

No clinical data on the safety or immunogenicity of the use of *Boostrix* during pregnancy or lactation have been generated. It is generally accepted that inactivated vaccines pose no risk to the pregnant or lactating woman [CDC, 2011d]. In the absence of supporting data, *Boostrix* should only be administered to pregnant women when clearly needed, and when the possible benefit outweighs the possible risks to the fetus. In the US, Tdap vaccination is recommended by ACIP in each pregnancy ([CDC, 2013a], see Section 7.1.3).

7.2. Rationale (Amended on 05 October 2017)

The purpose of this Registry is to detect and describe any abnormal pregnancy outcomes, including teratogenicity, in females intentionally or unintentionally exposed to *Boostrix* during their pregnancies **or within 28 days preceding conception**. The combination of the large number of women who are of reproductive capacity and may be exposed to tetanus, diphtheria, and pertussis; and the lack of data concerning exposure to *Boostrix* during pregnancy makes such a Registry an important component of the ongoing effort to assess the safety of *Boostrix*. The Registry was originally initiated on 03 May 2005, as part of a program of enhanced pharmacovigilance. Following new European Union Pharmacovigilance legislation, pregnancy registries are to be considered as PASS. The ongoing Registry *is* therefore converted into a PASS **in Q1 2014**.

The Registry requires voluntary, prospective reporting of eligible pregnancies by patients and HCPs. Patient confidentiality is strictly maintained. The intent of the Registry is to prospectively collect data describing exposure to *Boostrix* immediately before or during pregnancy, potential confounding factors (such as exposure to other medications), and information related to the outcome of the pregnancy.

8. RESEARCH QUESTION AND OBJECTIVES

8.1. Co-primary objectives

- To describe the characteristics of registered pregnancies (women vaccinated with *Boostrix* during pregnancy or within 28 days preceding conception) with any abnormal pregnancy outcomes.
- To assess the proportion of registered pregnancies (women vaccinated with *Boostrix* during pregnancy or within 28 days preceding conception) with any abnormal pregnancy outcomes.

Refer to Section 9.3.1 for the definition of the primary endpoint.

9. RESEARCH METHODS

9.1. Study design

9.1.1. Overview (Amended on 05 October 2017)

- This study is a transition of an ongoing pregnancy registry (starting on 03 May 2005) into a PASS.
- This is a prospective*, observational, exploratory, cohort study. The *Boostrix* pregnancy registry study requires voluntary, prospective reporting of eligible pregnancies by patients and HCPs. Data such as vaccination with *Boostrix* during pregnancy or within 28 days preceding conception, potential confounding factors (such as exposure to other medications) and information related to the outcome of the pregnancy will be collected prospectively**.

** Exposed pregnancies reported to the Registry before the transition into a PASS (between 03 May 2005 and Q1 2014), from which data were collected and analyzed prospectively, will also be included in the analyses.*

- *** Some pregnancy exposures may be reported after pregnancy outcome has been identified (retrospective reports). The Registry will capture retrospective reports, but these reports will not be included in the analyses of prospective reports.*
- Study population: pregnant women, vaccinated with *Boostrix* during pregnancy or within 28 days preceding conception, volunteering to take part in the study.
- Type of study: self-contained.
- Data collection: initial and follow-up data will be collected using questionnaires. ***Data for enrollment will be collected using the Initial Notification Form.*** Follow-up of cases is performed within 2 months of the estimated date of delivery (EDD) to ascertain ***pregnancy outcome (through the Pregnancy Outcome Form)*** and approximately 6 months and 12 months after the EDD (for all live births ***for whom the contact details of their HCP will be available***) to ascertain

the presence of birth defects not diagnosed before (*through the 6- and 12-month post-delivery Follow-Up Form*).

- After transition of the ongoing pregnancy registry into a PASS, data will be collected for a minimum of 5 years, starting Q1 2014.

9.1.2. Rationale for study design

This prospective cohort study is designed as a Registry. After market authorization, AEs that occur after administration of the vaccine can and should always be reported. In that case, however, there is no clear group in which the events occur and so a proper rate of occurrence cannot be estimated. In this pregnancy registry, participants are recruited between administration of the vaccine and the potential occurrence of an AE (i.e., a teratogenic effect in the offspring). This allows for a more proper estimation of the rate of occurrence of these events. Nevertheless, the results of this study still need to be regarded with caution as the exact number of women exposed during pregnancy is unknown. Incidences of events can therefore not be calculated from the study data.

Furthermore, it is likely that pregnant women who accept vaccination may differ from those who refuse vaccination in underlying health status, propensity to seek medical care, propensity to report AEs and differences in access to medical care in general. The differential response/participation by vaccinated versus unvaccinated pregnant women in a pregnancy registry could significantly bias risk estimates and possibly in unpredictable ways, because of the inability to collect adequate data to characterize the non-responders. Therefore, the risks of any identified birth defects will be compared to those in the general population, such as that defined by the Metropolitan Atlanta Congenital Defects Program (MACDP).

9.2. Setting

9.2.1. Study population

9.2.1.1. Patient population

In the US, *Boostrix* is indicated for active booster immunization against tetanus, diphtheria, and pertussis. Originally licensed for persons aged 10 through 18 years, the vaccine was approved by the FDA for use in persons aged 19 through 64 years in 2008, and in persons aged 65 years and older in 2011.

The study population includes women vaccinated with *Boostrix* during pregnancy or within 28 days preceding conception.

9.2.1.2. Potential annual exposure

Size of the potential “at-risk” population

The US Census Bureau estimates that, as of 1 July 2012, the resident US female population was 62,744,930 between the ages of 15 and 44 years old [US Census Bureau, 2013]. The provisional fertility rate in the US in 2012 was 63.2 births per 1000 women aged 15-44 years and the provisional count of births was 3.96 millions [CDC, 2012d].

Number of pregnant vaccinees

Boostrix was originally classified as FDA Pregnancy Category C, which was changed to Category B in September 2012, as a study of developmental toxicity in female rats showed no key safety concerns. Pregnancy Category B means that animal reproduction studies have failed to demonstrate a risk to the fetus and there are no adequate and well-controlled studies in pregnant women. Since February 2013, *Boostrix* vaccination is recommended by the ACIP in each pregnancy.

More than 20 million doses of *Boostrix* were distributed in the US between May 2005 and July 2011. Experiences with the ongoing *Boostrix* pregnancy registry (391 exposed pregnancies reported prospectively and five exposed pregnancies reported retrospectively between 03 May 2005 and 02 August 2013) and other vaccine pregnancy registries (e.g., smallpox vaccine [CDC, 2003], varicella vaccine [Shields, 2001], and *Twinrix*) indicate that it is likely that fewer than 100 pregnancies per year will be registered.

9.2.2. Patient recruitment (Amended on 05 October 2017)

Reporting of vaccine-exposed pregnancies to the Registry is voluntary. Since the initiation of the Registry in 2005, GSK has taken several measures to increase the rate of pregnancy registration (accrual). A GSK Registry web page has been created with instructions for enrolling patients in the Registry and GSK has requested that the FDA post a link to this web page on their Pregnancy Registry Website. ***The forms for enrolling and reporting outcomes are also accessible to healthcare providers through the GSK Registry web page.*** In response to a 2008 request from the FDA to facilitate enrollment, GSK initiated a dedicated toll-free telephone number (PPD [REDACTED]), at which US-based callers can receive assistance in the registration of pregnancies. Notice of this new toll-free number was posted on the GSK web page in January 2009; the new toll-free number was added to the US Prescribing Information in early 2009. The Prescribing Information and GSK Registry website each give a brief summary of the purpose and intent of the Registry, along with telephone contact information. ***Fax contact information is available on the GSK Registry web page.***

9.2.3. Selection of a comparison group

This registry study is a prospective cohort study. Active enrollment of a valid internal comparison group is not feasible. The outcomes of the study will be assessed against known rates from an external reference group for the likelihood of a safety signal

warranting further investigation. Background risks from existing, external systems (e.g., the National Birth Defects Prevention Network and the National Center for Health Statistics) will be used.

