9.3.2. Data to be collected (Amended 05 October 2017)

Initial and follow-up data will be collected using questionnaires. *Data for enrollment will be collected using the Initial Notification Form. Follow-up of cases is performed within 2 months of the estimated date of delivery (EDD) to ascertain pregnancy outcome (through the Pregnancy Outcome Form) and approximately 6 months and 12 months after the EDD (for all live births for whom the contact details of their HCP will be available) to ascertain the presence of birth defects not diagnosed before (through the 6- and 12-month post-delivery Follow-Up Form).* The following data will be collected:

- Patient identifier.
- Maternal data, including date of birth, date of last menstrual period (LMP), EDD.
- Maternal relevant medical/family history.
- Paternal relevant medical/family history.
- Type of conception.
- Prenatal testing.
- Maternal prenatal drug/vaccine exposure, including drug/vaccine name, date of administration, route of administration, dose, lot number, indication.
- Pregnancy outcome.
- Method of delivery.
- Infant/fetal information, including gestational weeks at birth/miscarriage/termination, gender, length, weight, Apgar score.
- Description of birth defects, if applicable.
- AEs experienced by the fetus/infant or the mother.
- Reporter information.
- Any additional data that seems relevant for this study.

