9.7. Data analysis (Amended on 05 October 2017)

Pregnancy outcomes include spontaneous abortion (pregnancy loss before 22 weeks gestation), fetal deaths/stillbirths (loss at or after 22 weeks gestation), elective/*induced* abortions and live births. Gestational weeks are counted from the date of the LMP. The second trimester is considered to begin at week 14 and the third trimester begins at week 28. The presence or absence of birth defects or other abnormalities is evaluated within each of the preceding outcome categories.

Pregnancy outcomes are stratified by the trimester of exposure, with an additional stratum for preconception exposure with no subsequent administration of vaccine during pregnancy. Reports of multiple exposures during a pregnancy (i.e., multiple administrations of *Boostrix*) are classified by the earliest trimester of exposure. When exposure occurs before and after conception, the exposure is classified by the dose administered after conception. The calculations of risk for birth defects are made by dividing the number of infants with birth defects by the total number of infants with and without birth defects. ***Given the descriptive nature of this study, confidence intervals will not be calculated.*** The outcomes of the study will be assessed against known rates from an external reference group for the likelihood of a safety signal warranting further investigation.

The majority of spontaneous abortions occur early in pregnancy [Wilcox, 1981; Wilcox, 1983; Elish, 1996]. If spontaneous abortions were to be evaluated as an outcome of interest, it would be essential to enroll pregnancies as soon as possible after vaccination with *Boostrix*. Because enrollment and recognition of pregnancy would occur at various times, it would be virtually impossible to meaningfully evaluate the effects of *Boostrix* on pregnancy loss [Kennedy, 2004]. Therefore, spontaneous abortions without birth defects are excluded from the risk calculations.

The risk in the general population of all birth defects meeting CDC criteria is approximately 3% (1 of 33) of live births [CDC, 2013b]. The estimated risk cited in the medical literature varies because of differences in case definitions, populations sampled and ascertainment methods. The Collaborative Perinatal Project, using a broader case

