10.2 Is the choice of statistical techniques described?				25-26
10.3 Are descriptive analyses included?				25-26
10.4 Are stratified analyses included?				25-26
10.5 Does the plan describe methods for adjusting for confounding?				25-26
10.6 Does the plan describe methods addressing effect modification?				

Comments:

Section 11: Data management and quality control	Yes	No	N/A	Page Number(s)
11.1 Is information provided on the management of missing data?				
11.2 Does the protocol provide information on data storage? (e.g. software and IT environment, database maintenance and anti-fraud protection, archiving)				24, 27, 28
11.3 Are methods of quality assurance described?				27

Section 11: Data management and quality control	Yes	No	N/A	Page Number(s)
11.4 Does the protocol describe possible quality issues related to the data source(s)?				
11.5 Is there a system in place for independent review of study results?				

Comments:

--

Section 12: Limitations	Yes	No	N/A	Page Number(s)
12.1 Does the protocol discuss:				
12.1.1 Selection biases?				20, 27
12.1.2 Information biases? (e.g. anticipated direction and magnitude of such biases, validation sub-study, use of validation and external data, analytical methods)				20, 27

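### The birth-defect comparison with general-population rates is unadjusted for maternal age or anything else, while checklist item 10.5 says adjustment methods are described

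*Combined protocol and SAP*

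**What the plan says.** **Comparator.** Section 9.1.2 says that "the risks of any identified birth defects will be compared to those in the general population", and gives the Atlanta surveillance programme as an example. Section 9.2.3 adds: "Background risks from existing, external systems (e.g., the National Birth Defects Prevention Network and the National Center for Health Statistics) will be used". Section 9.9 repeats this and leaves the limits of such comparisons to ad hoc discussion in the periodic reports.

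**Estimator.** Section 9.7: "The calculations of risk for birth defects are made by dividing the number of infants with birth defects by the total number of infants". The denominator thus counts affected and unaffected infants together. The only stratification is by timing of exposure: "Pregnancy outcomes are stratified by the trimester of exposure, with an additional stratum for preconception exposure". On precision: "Given the descriptive nature of this study, confidence intervals will not be calculated".

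**Use of the comparison.** The aggregate review criteria in section 9.7 ask whether all defects, and separately individual defects, depart from their expected frequencies. Section 9.2.3 ties the external comparison to the likelihood of a safety signal.

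**Age.** Section 9.3.2 collects "Maternal data, including date of birth, date of last menstrual period (LMP), EDD". Section 9.2.1.1 gives the licence history: "Originally licensed for persons aged 10 through 18 years", extended to ages 19 through 64 in 2008 and to 65 and over in 2011. Section 9.2.1.2 puts the recommendation for each pregnancy at February 2013. Section 9.7 includes prospective reports from May 2005 onward in the analyses.

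**Checklist.** Annex 2 asks "10.5 Does the plan describe methods for adjusting for confounding"; the answer is Yes, pages 25-26.

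**The concern.** When an external rate is the only yardstick, the expected frequency is right only if the reference population resembles the registry in whatever drives the outcome. Maternal age is an obvious candidate. Section 9.6.2.2 counts chromosomal abnormalities as birth defects, and the protocol's account of the controlled Tdap cohort in section 7.1.2 reports maternal age in both groups. Because eligibility by licence and the recommendation in pregnancy both changed while reports were being pooled, there is a concrete reason to ask whether the registry's mothers resemble US mothers overall, and whether they did so equally in 2006 and 2016.

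If they do not, an age difference could produce an apparent departure from the expected frequency, or cover a real one. The checklist adds a second problem: it tells a regulator that the plan contains a method which section 9.7 does not describe.

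**Working it through.** The plan states no figure for this comparison that could be reproduced, so the check is mainly textual.

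**Step 1: is any adjustment planned?** Sections 9.2.3, 9.7 and 9.9 contain no standardisation, matching, regression or age stratum. The nearest item is a question in section 9.7 about another known or likely cause. It applies to individual reports and does not change an expected rate.

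**Step 2: can the Yes at item 10.5 be explained?**
- *By stratification on exposure timing?* Item 10.4 already covers stratified analyses, and trimester of exposure describes the exposure. It does not adjust for differences from the reference population.
- *By collecting confounders?* Section 9.1.1 says potential confounders are collected but attaches no analysis method. Item 7.1, on addressing known confounders, points elsewhere (pages 22 and 23).
- *By old page numbers?* Annex 1 dates the checklist 06 March 2014, before the amendment. The changes to section 9.7 logged in Annex 4 alter the gestational cut-off and the abortion wording and remove the exact confidence interval. No adjustment method was removed.

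None of these explains the tick.

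**Step 3: can the age effect be sized?** With *n* infants, registry age shares *p*, reference age shares *w* and age-specific risks *r*:
- crude expected count = n × Σ w·r
- age-standardised expected count = n × Σ p·r
- difference = n × Σ (p − w)·r, which for two age bands is n × (p₁ − w₁) × (r₁ − r₂)

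The difference is zero if the age mixes agree or if risk does not vary with age. Otherwise its sign depends on both factors. The documents give an overall risk of about 1 in 33 (section 9.7) and 391 prospective reports by 2 August 2013 (section 9.2.1.2). They give no *w* and no age-specific *r*, and the text available gives no *p*. Part of section 7.1.2 was not available, so registrant ages cannot be said to be absent from the full protocol. Neither size nor direction can be stated.

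**Step 4: how much data would the table hold?** Treating the 391 reports as 391 infants with known outcome, the crude expected count is 391 ÷ 33 = 11.8 defects. Chromosomal defects are a subset of these, so cells by age band will be sparse.

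For the early period, 391 reports over 8.25 years is 47.4 a year. If accrual was uniform (an assumption), 3 May 2005 to the end of 2008 is 3.67 years, or about 174 reports and 174 ÷ 33 ≈ 5 expected defects. That is too few to justify requiring a separate pre-2008 analysis by age band.

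**The case against.** **The study is exploratory and descriptive.** It has no minimum sample size and no confidence intervals, and sections 9.1.2 and 9.9 concede selection bias. This stands, and it limits the consequence. But the plan still asks whether defect frequency departs from expectation, and neither section names age.

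**The age effect may be small beside other problems.** This also stands. Section 9.7 gives background risks of about 3% and, under a broader definition, 5% to 7%. For 391 infants these give 11.8, 391 × 0.05 = 19.6 and 391 × 0.07 = 27.4 expected defects. Age standardisation does not resolve that spread. The early reports are also a minority by the August 2019 lock: with the 174 above and six further years at 47.4 to 100 reports a year, 174 ÷ 675 = 26% down to 174 ÷ 991 = 18%.

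**Stronger readings that the documents do not support:**
- *That licensing changes did shift the registry's age mix.* Reporting is voluntary and covers intentional and unintentional exposure, so the licensed range does not fix registrants' ages.
- *That one overall rate is applied.* Section 9.7 also compares individual defects, and several reference systems are named. Those comparisons are equally unadjusted.
- *That date of birth is never used.* The first co-primary objective could include describing maternal age. That objective covers only pregnancies with abnormal outcomes, however, so it would not supply the age distribution of the denominator.
- *That age distorts the comparison through fetal loss.* Spontaneous abortions without defects are excluded from the risk calculation.

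**Conclusion.** Two facts are established from the text: the planned external comparison is crude, and the Yes at checklist item 10.5 has no counterpart in section 9.7. That maternal age biases the comparison is a plausible possibility only. It rests on the changing licence and recommendation, the pooling of reports since 2005, and the inclusion of chromosomal abnormalities.

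A reader might want to attach a percentage to the bias. Any such figure would need the registry's age shares and age-specific reference risks, which are not given, so none is offered. The effect could be negligible. This is a cheap improvement to how the expected frequency is formed. It does not invalidate a descriptive registry.

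**What to change.** In section 9.7, with a cross-reference from 9.2.3:

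1. Tabulate maternal age, from the date of birth already collected, for all infants in the risk denominator. Use the reference system's definition of maternal age and show missing ages as their own row.
2. Where the reference publishes maternal-age-specific rates, report observed and indirectly standardised expected counts by age band (for example under 20, 20 to 34, 35 and over), for all defects and for chromosomal defects. Expected count = sum over bands of registry infants × reference rate. Keep the crude comparison beside it.
3. Where no age-specific rate exists, show the crude comparison only and say so.
4. Reconcile Annex 2 item 10.5 with section 9.7: point it to the new text, or change the answer.

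A mandatory split before and after 2008 is not needed.

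**Cost.** One paragraph, one extra table and a checklist correction, with no new data collection. The downsides are sparse cells and some defects that keep the crude comparison for want of age-specific reference rates.

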9.2.4. Study period (Amended on 05 October 2017)

The Registry was originally initiated on 03 May 2005, as part of a program of enhanced pharmacovigilance, and converted into a PASS *in Q1 2014*. GSK plans to continue the Registry for a minimum of 5 years, starting Q1 2014. After submission of the final report, GSK will continue the Registry pending CBER review of the report and determination whether the Registry can be discontinued.

